## **Study Protocol**

Initial efforts for relationship building with a school system have already begun; the PI recently concluded a pilot yoga study in March of 2019 at Park High School, and school and district leadership have expressed a keen interest in continuing this type of intervention for students. For example, in the coming academic year, the school would like to implement this proposed research study, focusing on increasing the number of student participants while gathering additional data for continuous program improvement. [name], district administrator with Park County schools, has also expressed a desire in continuing this research and eventually expanding it to other schools in the district in collaboration with the PI.

In the September 2019, the PI will facilitate a focus group discussion of both male and female high school students at Park High School to gauge student interest in the project and determine best approaches to promote recruitment and retention in the project (particularly with male students). These focus groups will be facilitated through the “Principal Advisory” lunchtime program with the high school principal and PI. Following the focus group discussions, high school participant recruitment will begin with school administrator recommendation for inclusion in the project, and those students will be offered slots in the program first; to allow for maximum recruitment and retention, the intervention will begin in late Fall 2019 between athletic seasons/events. 30-minute sessions will take place twice weekly during the physical education class during the 8-week intervention period. After students have been given an option for inclusion, the program will accept any additional voluntary participation by students within the school, and program recruitment will conclude by the end of 2019.

Participation will be voluntary and will be indicated by student signature of the assent form; parent consent will also be required for student participation in this 8-week study. The 30 students to be enrolled in the program will provide written informed consent regarding the scope and details of the study and procedures for participating in the study. The consent form and assent form will include information about participants’ rights to end participation at any time during the study.

Incentives for teacher completion of surveys include classroom supply money for teacher completion of surveys (funneled through school administration).

It is possible that the intervention may bring up strong emotions for the participants; so too might the administration of the ACE survey which will be part of the preliminary data collection (more below). To mitigate this potential, the PI will caution students that this may occur and emphasize the importance of self-care and knowing one’s own limits with the intervention. Immediate referrals regarding suicidality, self-harm, depressive thoughts, etc. will be directed to the school nurse. If needed, referrals for additional, outside treatment will be provided as determined by school officials and/or requested by the participant and/or the participant’s legal guardian(s). It will also be explained to participants that this study is not designed to be a clinical/psychological intervention but rather an academic intervention, so students that need additional mental health supports will be referred to appropriate outside agencies.

Additional resources for outside assistance will be shared with participants and participant parents/guardians on the assent/consent forms, listing the following avenues for additional help:

- Talking with someone who you can trust
- Calling 911, your doctor or other healthcare provider
- Going to an Emergency Room
- Calling [name] to talk with a crisis worker for free
- Texting 741741 to text with a counselor for free

Visiting [NowMattersNow.org](http://NowMattersNow.org) to learn skills for dealing with thoughts of suicide

## **Methods**

Initial efforts for relationship building with a school system have already begun; the PI recently concluded a pilot yoga study in March of 2019 at Park High School, and school and district leadership have expressed a keen interest in continuing this type of intervention for students. For example, in the coming academic year, the school would like to implement this proposed research study, focusing on increasing the number of student participants while gathering additional data for continuous program improvement. [name], district administrator with Park County schools, has also expressed a desire in continuing this research and eventually expanding it to other schools in the district in collaboration with the PI.

In the September 2019, the PI will facilitate a focus group discussion of both male and female high school students at Park High School to gauge student interest in the project and determine best approaches to promote recruitment and retention in the project (particularly with male students). These focus groups will be facilitated through the "Principal Advisory" lunchtime program with the high school principal and PI. Following the focus group discussions, high school participant recruitment will begin with school administrator recommendation for inclusion in the project, and those students will be offered slots in the program first; to allow for maximum recruitment and retention, the intervention will begin in late Fall 2019 between athletic seasons/events. 30-minute sessions will take place twice weekly during the physical education class during the 8-week intervention period. After students have been given an option for inclusion, the program will accept any additional voluntary participation by students within the school, and program recruitment will conclude by the end of 2019. Participation will be voluntary and will be indicated by student signature of the assent form; parent consent will also be required for student participation in this 8-week study. The 30 students to be enrolled in the program will provide written informed consent regarding the scope and details of the study and procedures for participating in the study. The consent form and assent form will include information about participants' rights to end participation at any time during the study.

Incentives for teacher completion of surveys include classroom supply money for teacher completion of surveys (funneled through school administration).

It is possible that the intervention may bring up strong emotions for the participants; so too might the administration of the ACE survey which will be part of the preliminary data collection (more below). To mitigate this potential, the PI will caution students that this may occur and emphasize the importance of self-care and knowing one's own limits with the intervention. Immediate referrals regarding suicidality, self-harm, depressive thoughts, etc. will be directed to the school nurse. If needed, referrals for additional, outside treatment will be provided as determined by school officials and/or requested by the participant and/or the participant's legal guardian(s). It will also be explained to participants that this study is not designed to be a clinical/psychological intervention but rather an academic intervention, so students that need additional mental health supports will be referred to appropriate outside agencies.

Additional resources for outside assistance will be shared with participants and participant parents/guardians on the assent/consent forms, listing the following avenues for additional help:

- Talking with someone who you can trust
- Calling 911, your doctor or other healthcare provider
- Going to an Emergency Room
- Calling [name] to talk with a crisis worker for free
- Texting 741741 to text with a counselor for free

Visiting NowMattersNow.org to learn skills for dealing with thoughts of suicide

**Aim 1:** Foster a partnership with a rural southwestern Montana school and test the feasibility of implementing a trauma-informed yoga intervention.

For this pilot study, feedback will be gathered from the school district, teachers, and students from the focus group via conversations and/or email communications to determine the level of burden from the various assessment instruments and participation in the pilot; plans and identified needs for this study are ongoing with the school district and the PI. Retention and satisfaction of participants, as measured by survey instrumentation) from year one will indicate the feasibility of an ongoing partnership with the school district, determine possible expansion to the middle school in year two, and will assess both students' and teachers' perception of value of the intervention. Because this is a feasibility study, no control group will be utilized, and the focus of the project will be to examine pre and post survey results and cortisol levels.

**Aim 2:** Collect preliminary data for the intervention (surveys, interviews and cortisol levels) to assess effectiveness of the intervention to improve youth mental and physical health (e.g., behavioral, social, emotional, and physical functioning).

*Sources of Materials.* Assessment measures will include the: 1) Adapted ACE Self-Reporting Screener (which will only be given pre-intervention to determine ACE scores of participants) 2) "Toolkit" of validated survey measures to assess academic, social, and emotional functioning of adolescents across multiple domains; 3) Teacher Perceptions of Student Wellness Pre- and Post-Surveys, 4) Cortisol levels before, during, and after the intervention period, 5) Collection of reflective journals from the group participants, and 6) Collection of secondary behavioral and academic data (grade averages in reading and math, attendance, and office referrals).

The "toolkit" of validated student pre and post surveys includes the following measures:

To assess academic functioning:

- Engagement (Simons-Morton & Crump, 2002)

- Class Absences and School Misbehavior (adapted from Kessler, 2001)

To assess emotional and social functioning:

- Depressive Symptoms (SMFQ) (Adrian Angold & Elizabeth J. Costello, 1987)
- Generalized Anxiety Disorder 7-item (GAD-7) scale (Spitzer et al., 2006)
- Loneliness (Hughes et al., 2004)
- Difficulties in Emotion Regulation Scale (Neumann et al., 2010)

Teacher Perceptions of Student Wellness Surveys (rated on a Likert Scale of 1-5) include questions before and after program implementation relating to academic, emotional, and social functioning as well. Examples of survey questions include items assessing individual students, such as whether they are “in control of their behavior (e.g., less reactive),” “can concentrate on work,” and “can deal appropriately with stress and anxiety (e.g., during test-taking or similar events).” Teachers will be given an incentive of \$25 in classroom supply money (funneled through school administration) for the completion of each pre and post survey for each of the student participants.

To protect student privacy, the ACE screening instrument will only quantify how many adverse events the child has experienced, **not** which ones; quantifying ACE scores will help the researcher triangulate the data to determine program efficacy for students with high, moderate, and low ACE scores. School and district administration will have access to anonymous ACE scores for the purpose of collecting demographic information on the participant population. The remainder of the anonymous data collected will be analyzed and reviewed by the community advisory board; decisions regarding program improvement, future implementation, and modifications will be made by the advisory board as well.

For all participants, the primary behavioral health assessments will utilize descriptive statistics and paired t tests with regards to the validated “toolkit” survey of students to address academic, social, and emotional functioning of adolescents (including measures such as the Generalized Anxiety Disorder Scale and Patient Health Questionnaire for Depressive Symptomology) and a Teacher Perception of Student Wellness Survey to assess changes pre-and post-intervention. Descriptive statistics will be utilized with health outcomes to compare pre-and post-intervention cortisol levels. Any secondary academic outcomes will also be analyzed descriptively pre-and post-intervention, as improvement in academic performance may serve as a proxy for improved well-being (attendance records pre-, during, and post-intervention (absences and times arriving late to school), office referral data prior to, during, and post-intervention, and grade average data based on numerical averages in students’ reading and math courses pre- and post-intervention). Baseline data regarding participants’ exposure to childhood trauma as measured by the ACE Self-Reporting Screener will be gathered to determine any relationships between individual ACE scores and outcomes from intervention.

To allow all who are interested to participate in the study, the focus of this project will primarily be to determine feasibility of the intervention; therefore, no control group will be utilized, and the focus of the feasibility trial will be to examine pre and post survey results and cortisol levels. Volunteers will participate in the intervention for 8 weeks. During the intervention phase, the participation goal for each student will be to attend 75% or more of the intervention sessions (attendance will be recorded by the yoga instructor).

After students volunteer for program participation, to establish a baseline for participants, students will be given the ACE screening instrument/ toolkit of pre-surveys and then begin the 8-week intervention. Students will be administered cortisol testing at the beginning of weeks 1 and 4 and the conclusion of week 8 during the intervention, each time prior to the yoga session, and they will complete the post surveys at the conclusion of week 8. At each of the three testing periods, students will provide a saliva sample to the school nurse or PI, to be deidentified (using a code key system) before analysis by the CAIRHE Translational Biomarkers Core Lab at MSU. Testing will use the Abcam (ab154996) cortisol in vitro competitive ELISA (Enzyme-Linked Immunosorbent Assay) kit designed for the accurate quantitative measurement of cortisol in saliva (sensitivity 0.12 ng/ml). Deidentified cortisol data will be returned to the PI for re-identification using the code key. Comparisons using paired t tests between pre and post-surveys will be utilized to determine program efficacy, and any changes in cortisol levels throughout the duration of the program will be analyzed to assess any trends and whether this is a useful measure for the next study phase.

**Aim 3:** Use the preliminary data to modify (as needed) year two of the study for expansion to middle level students and/or increasing the number of high school participants.

This study will utilize descriptive statistics for pre- and post-interventions and analysis of cortisol levels throughout the program to determine the efficacy the intervention.

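### Student feedback on burden is drawn from a focus group convened before recruitment, whose members need not have taken part in the study

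*Combined protocol and SAP*

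**What the plan says.** Three parts of the document bear on this.

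- **Source of burden feedback (Methods, Aim 1).** The plan states that "feedback will be gathered from the school district, teachers, and students from the focus group via conversations and/or email communications", and that the aim is "to determine the level of burden from the various assessment instruments and participation in the pilot". The sentence gives no date and no set of questions.
- **The focus group (Study Protocol, repeated in Methods).** The discussion is set for September 2019 and is held "to gauge student interest in the project and determine best approaches to promote recruitment and retention in the project". It runs through an existing "lunchtime program with the high school principal and PI". Burden is not among its stated purposes.
- **Entry to the study (same sections).** "Following the focus group discussions, high school participant recruitment will begin with school administrator recommendation for inclusion in the project". After the recommended students have been offered places, "the program will accept any additional voluntary participation by students within the school". Enrolment is set by "The 30 students to be enrolled in the program".

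From participants, Aim 1 takes other feasibility measures: "Retention and satisfaction of participants, as measured by survey instrumentation) from year one will indicate the feasibility". Aim 2 adds surveys, cortisol, journals and, in its opening statement, interviews. Session attendance is recorded against a 75% goal.

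**The concern.** Burden is something that a student who has gone through the study can report and a student who has not can only guess at. What is asked of an enrolled student is considerable: the ACE screener, a toolkit of six listed measures given before and after, three saliva samples, a reflective journal, and two sessions a week for 8 weeks. The protocol itself warns that the ACE survey and the intervention may stir strong emotions.

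The only students named as a source on burden belong to a group formed for another purpose, before anyone was recruited. If the plan is followed as written, the Aim 1 statement on student burden may describe expectation rather than experience, and a reader of the results could not tell which. Feasibility is the declared main focus of the project, and under Aim 3 the preliminary data are to be used to modify year two. A burden finding from the wrong students would be a weak guide to that.

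**Working it through.** No figure for burden is stated in the plan, so there is none to reproduce. The check compares the passages with one another.

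1. **Which focus group is meant?** The term is used only for the September 2019 discussion (the text moves between singular and plural). No focus group of enrolled students, and no discussion during or after the 8 weeks, is described. Where Aim 2 means the enrolled students, it calls them group participants.

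2. **Does membership lead to enrolment?** Recruitment follows the discussion. There are two routes in: administrator recommendation, then open volunteering. Membership of the focus group is neither a route nor a condition. A member may enrol, but nothing requires it, and an enrolled student need not have been a member.

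3. **How large could the overlap be?** Let *g* be the number of focus-group students and *m* the number of them who enrol. The plan fixes only the 30 enrolled, so 0 ≤ *m* ≤ min(*g*, 30).
   - Share of enrolled students inside the stated source: *m*/30.
   - Share of enrolled students outside it: 1 − *m*/30.
   - At *m* = 0, this is 1 − 0/30 = 100%: no enrolled student is in the stated source.
   - At *m* = *g* (the whole group enrols, with *g* ≤ 30), every focus-group respondent has been enrolled, but 30 − *g* enrolled students are still outside the source.

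   Neither *g* nor *m* is given, so the range cannot be narrowed.

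4. **How much exposure does a non-participant lack?** Sessions: 2 per week × 8 weeks = 16. The 75% goal is 0.75 × 16 = 12 sessions. Saliva: the start of weeks 1 and 4 and the end of week 8, so 3 samples. A focus-group student who does not enrol has none of this.

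5. **Does another planned measure cover burden?**

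| Planned measure | Where | Assigned to burden? |
|---|---|---|
| Retention, satisfaction survey | Methods, Aim 1 | No; tied to continued partnership, possible expansion and perceived value |
| Interviews | Aim 2 opening statement | No; content not given |
| Reflective journals | Aim 2, list of measures | No |
| Session attendance | Methods, Aim 2 | No; participation goal, and a covariate in the SAP |
| Pre and post surveys, cortisol | Aim 2 and SAP | No; outcome measures |

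The Statistical Analysis Plan has no burden analysis. Its pre-post comparisons use students with both time points, and no exit questions for students who stop are described.

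**The case against.** The strongest reply is that the Aim 1 sentence is undated. Feedback by conversation and email is a different channel from the lunchtime discussion, so it could be a later follow-up with focus-group members who did enrol. It could equally be early input on expected burden while plans with the district were still being made, and students who have not enrolled can properly give that. Both readings are open. Neither removes the gap: under the first, nothing ensures that members enrolled or that the other enrolled students are heard; under the second, no measure of students' experienced burden is assigned.

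It is also fair to say that the sentence names teachers and the district. Teachers complete the pre and post surveys and can report their own burden from experience. The point is therefore confined to student burden.

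A reader might go further in four ways that the documents do not support.

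- *The answer will be biased toward low burden because the group was selected for interest.* The group is held to find out how much interest there is, which is not selection on interest. Students without exposure could overstate burden as easily as understate it.
- *The respondents have no exposure.* The overlap is unknown, so this is possible but not established.
- *Participants have no way to report burden.* The content of the satisfaction survey and interviews is not given, and journals are open to such comments. What can be said is that none of these is assigned to the task.
- *The year-two decision turns on burden.* Aim 1 ties expansion to retention and satisfaction. Aim 3 refers to the preliminary data in general, and no decision rule depends on burden.

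**Conclusion.** The point holds for student burden. The stated student source is a group convened before recruitment, with no link to enrolment, so the feedback may come partly or wholly from students who did not experience the instruments or sessions. The proportion is unknown, anywhere from none to all of the group, and so is the direction of any bias.

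This rests on two readings: that the focus group named in Aim 1 is the September 2019 one, which is the only one described, and that measures not assigned to burden are not meant to serve it. If the authors meant the enrolled students, the sentence still needs correcting.

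It is more than missing detail, because the plan names a source and that source is poorly matched to the question. It does not affect the pre-post analyses or any formal decision rule. It should be changed, and the change is small.

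**What to change.** Amend the Aim 1 sentence so that student burden feedback is collected from all enrolled participants. Add a few short items to the week-8 post-survey, asking separately about the surveys, the saliva sampling and the sessions. Offer the same items at exit to students who stop and are willing to answer. Keep the district and teachers as sources, and keep the September focus group for planning recruitment and retention.

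The cost is one revised sentence, a few added items and slightly more survey time for each student.

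### One example item in the teacher survey pairs a state stem with a comparative gloss that has no reference point, so its ratings before and after the programme may not measure the same thing

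*Combined protocol and SAP*

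**What the plan says.** Aim 2 in the Methods lists teacher surveys among the assessment measures. They are "rated on a Likert Scale of 1-5" and "include questions before and after program implementation relating to academic, emotional, and social functioning as well". The text then illustrates the content: "Examples of survey questions include items assessing individual students, such as whether they are" "in control of their behavior (e.g., less reactive"). Two further examples follow: "can concentrate on work" and "can deal appropriately with stress and anxiety (e.g., during test-taking or similar events").

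Later under Aim 2, the primary behavioral health assessments are to be analysed with descriptive statistics and paired t tests, and they include "a Teacher Perception of Student Wellness Survey to assess changes pre-and post-intervention". The same section adds: "Comparisons using paired t tests between pre and post-surveys will be utilized to determine program efficacy". There is no control group. The Statistical Analysis Plan section does not mention the teacher survey by name.

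**The concern.** A difference between two ratings can be read as change only if the question means the same thing both times. The gloss on the first example item is a comparative without a stated comparator. A teacher answering at baseline could compare the student with classmates, with the start of the year, or with nothing in particular. A teacher answering at week 8, knowing that the student has just finished a yoga programme, has an obvious comparator: the same student before the programme. The first answer would then tend to be a rating of state and the second a rating of perceived improvement. The later wording also names the hoped-for direction.

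The design has nothing that would expose such an artefact. Without a control group, a shift produced by the wording cannot be told apart from a shift in behavior. The documents do not describe blinding of the teachers. The student toolkit is described as validated, but the teacher survey is not. At stake is whether this item's contribution to the teacher results can be interpreted, in a study whose preliminary data are to shape year two (Aim 3).

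**Working it through.** The point concerns wording. The plan gives no figure to reproduce, so the check sets the relevant statements side by side.

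**Inputs, all from Methods, Aims 1 and 2**

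- Stem of the item: a present state (being in control of behavior).
- Gloss of the item: a comparative (less reactive), offered as an example, with no comparator.
- The other two example items: plain states, neither with a comparative.
- Timing: before and after the programme.
- Use: change from before to after, with paired comparisons read as efficacy.
- Control group: none.
- Scale: 1 to 5, anchors not given.
- Not given: the form itself, the number of items, the recall window, the scoring rule, any separate wording for the two administrations.

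**Step 1. Is the item ratable at baseline?** Yes. The stem says what is to be rated. The gloss makes the answer ambiguous but does not remove its object.

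**Step 2. Could the meaning shift between administrations?** Yes. If a teacher relies on the stem both times, or reads the gloss loosely as *not very reactive*, both ratings are states and the difference is change. If the teacher relies on the gloss at follow-up and reads it as *less than before*, the follow-up rating is an improvement rating and the difference is not change. The documents contain nothing that rules out the second reading: no comparator, no recall window, and no statement that the gloss is dropped at baseline.

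**Step 3. Can the direction of the effect be derived?** No. Suppose, purely as an assumption, that 3 on the follow-up scale means *no different from before*. A student who has not changed and was rated *s* as a state at baseline then shows a spurious difference of 3 − *s*:

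| Baseline state rating *s* | Spurious difference, 3 − *s* |
|---|---|
| 1 | +2 |
| 2 | +1 |
| 3 | 0 |
| 4 | −1 |
| 5 | −2 |

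Averaged over students, this is 3 minus the mean baseline rating. It is a gain if that mean is below 3 and a loss if it is above. The documents give neither the anchors nor any baseline distribution, so neither the sign nor the size follows.

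**Step 4. Is consistent state wording feasible?** Yes. The two other example items already use it.

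**The case against.** Several points on the other side are sound.

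- The item as a whole is not worded as a change. A reader might infer that the baseline rating has no referent at all. The documents do not support that: the stem supplies one, and only the parenthetical example is comparative.
- Identical wording at both administrations is an inference. The text gives examples in a running sentence and does not reproduce the form, which may already state a time frame. The inference is reasonable, because the examples are introduced for a before-and-after survey without separating two versions. If the versions do differ, their scores are not directly comparable, so confirmation is needed either way.
- A reader might also infer that the teacher score is biased toward improvement. This is not shown. The same mechanism can produce false losses, and one gloss in a form of unknown length says little about a total score.
- Lack of blinding and of a control group are features of the disclosed feasibility design. Rewording an item would not remove teachers' expectations.
- The study is primarily about feasibility, and the teacher survey is not among the outcomes named for the ANCOVA. This lowers the stakes. It does not remove them, because the Methods include the teacher survey among the primary behavioral health assessments and read paired survey comparisons as efficacy.

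What survives is narrow: the gloss has no reference point, and on this item the difference between the two ratings is open to two readings.

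**Conclusion.** The concern holds in a limited form and is minor. The example item mixes a state stem with a comparative gloss in a survey used to measure change. The two ratings on that item may not measure the same thing, and the follow-up rating may be nudged by the wording. The conclusion assumes that the gloss appears on the form much as it does in the protocol, and at both administrations. No bias can be sized or signed, and the number of affected items is unknown beyond one of the three examples shown. The documents do not support a claim that the teacher survey as a whole is invalid.

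**What to change.** Replace the gloss with a non-comparative one, for example *does not react impulsively*, and do the same for any other comparatively worded item on the form. Use identical wording, recall window and anchors at both time points, and state them in the protocol. If the investigators want teachers' impressions of change, ask that question once, after the programme, and report it separately from the before-and-after score.

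Some of the Statistical Analysis Plan is written in the past tense, so the form may already be in use. If baseline ratings have been collected, do not change the wording partway through. Keep it for that cohort, report this item separately from the rest of the teacher score, and reword it for year two.

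The cost is an edit to a form, with no extra participants, visits or analyses if made before first use. The one small downside is that the item will no longer match any earlier version of the form.
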